10. SUBJECT WITHDRAWAL

Subjects have the right to withdraw from the study at any time, for any reason, without jeopardizing their medical care. To prevent premature withdrawal from the study each participant will be properly informed about the study procedures and visits before his/her enrollment. Each case of premature withdrawal will be properly recorded. Wherever possible, subjects will be followed for safety and will be encouraged to return for follow-up visits and for any unresolved adverse events.

No subject will be removed from the study unless the subject has withdrawn his/her consent before treatment or no treatment was ever attempted.

Subjects withdrawn from the study, for any reason, who have not completed the 6-month followup visit, will be replaced by enrollment of additional subject. In any case, no more than additional 20% of the original study size will be enrolled.

The Royal	Document No.	Version	Document Date	Author	Page: 35
Wolverhampton NHS Trust	CIP Study No. 2019OPH108	1.6	03 August 2021	[name]	Out of: 60

11. ASSESSMENT OF STUDY PARAMETERS

11.1 MEASUREMENT OF INTRAOCULAR PRESSURE

Goldmann applanation tonometry (GAT) is considered the gold standard for IOP measurement; its accuracy is, however, influenced by corneal thickness, curvature, and biomechanical properties, such as rigidity, viscosity, elasticity, hydration, which have shown to have high interindividual variability and to be affected by corneal pathology and surgery.

The iCare is a new handheld tonometer, which is based on the impact-induction principle also known as rebound tonometry. The main advantages of this device include its quick and simple use, and that local anesthesia and slit lamp are not needed. The iCare tonometer has shown good reproducibility and correlation with GAT and is designed not to be influenced by corneal properties.

In iCare rebound tonometer, a very light-weight probe is used to make a momentary contact with the cornea. In the rebound technology, motion parameters of the probe are recorded during the measurement. An induction based coil system is used for measuring the motion parameters. An advanced algorithm combined with the state of the art software analyzes deceleration and the contact time of the probe while it touches the cornea. Deceleration and the contact time of the probe change as a function of IOP. In simple terms, the higher the IOP, the faster the probe decelerates and the shorter the contact time.

Alternatively, other standard tonometers can be used to measure the intraocular pressure.

Intraocular pressure will be measured at baseline and at each follow-up visit.

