5.2.2 SECONDARY SAFETY ENDPOINTS

The following secondary safety endpoints have been determined and will be systematically documented in the Case Report Form for each patient visit:

- Changes in IOP during observation period
- Changes in corneal transparency and lenticule transparency during observation period
- Inflammation of cornea or sclera during observation period
- Changes to the corneal epithelium during observation period
- Changes to conjunctiva, iris/pupil, lens during observation period
- Changes to ocular pain/discomfort during observation period

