7.2 EXCLUSION CRITERIA

Candidates for participation will be ineligible for the study if any of the following conditions apply:

- History or presence of any ocular pathologies that may interfere with the planned surgical treatment, including corneal epithelial problems
- Previous corneal transplantation or corneal implant in the designated eye
- Cataract with anticipated surgical intervention (IOL implantation) within 2 years
- Active inflammation and/or infection of the eye or the eye lid
- Patients with IOP <10 mmHg or >21 mmHg
- Professionally diagnosed and currently treated autoimmune diseases
- Current strong symptoms of any allergy
- History of major organ transplantation and/or current continuing immunosuppressive treatment
- History of blood transfusion within the last 12 months

The Royal	Document No.	Version	Document Date	Author	Page: 23
Wolverhampton NHS Trust	CIP Study No. 2019OPH108	1.6	03 August 2021	[name]	Out of: 60

• Subject who is currently participating or has participated in another investigational clinical study within the past 60 daysPregnancy and lactation

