14. RISK BENEFIT ANALYSIS

14.1 BENEFITS

The purpose of this clinical investigation is to evaluate the safety of implanting the Gebauer™ Lenticule in subjects with keratoconus or post-LASIK ectasia.

The Gebauer[™] Lenticule device is indicated for use as an implantable device, which shall change the thickness and surface curvature of the patient's cornea so that a change in corneal thickness and refraction is induced.

The Gebauer[™] Lenticule has several advantages in treating keratoconus and post-LASIK ectasia as compared to alternative treatment options as described in Chapters 2.1 and 2.2. above:

• The GebauerTM Lenticule is a transparent, biocompatible corneal implant which can be

The Royal	Document No.	Version	Document Date	Author	Page: 40
Wolverhampton NHS Trust	CIP Study No. 2019OPH108	1.6	03 August 2021	[name]	Out of: 60

expected to mechanically stabilize the diseased corneal tissue without impairing the patient's vision nor his/her intraocular pressure

- The implanted collagen fibers are similar to the collagen fibers present in the natural human corneal stroma. Therefore, the implant material is expected to be fully accepted by the corneal tissue and to be integrated in its metabolism
- As the Gebauer[™] Lenticule is devoid of foreign cellular components such as cell walls, foreign proteins, lipids and foreign genetic information (DNA/RNA), the risk of immuno-logical rejection is much lower than for human cornea donor tissue transplantation.

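### Section 11.1 lets the tonometer vary within a subject although the implant is meant to alter the corneal properties said to affect Goldmann readings, so IOP change may be partly a measurement shift

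*Protocol*

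**What the plan says.** Section 5.2.2 lists "Changes in IOP during observation period" among the secondary safety endpoints. Section 13.7.4 names IOP as an example of a variable whose change may be modelled over time with baseline as covariate, giving adjusted means, 95% confidence intervals and a test of change against zero at each time point.

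Section 11.1 calls Goldmann tonometry the gold standard but says that "its accuracy is, however, influenced by corneal thickness, curvature, and biomechanical properties", and that these properties have been shown "to be affected by corneal pathology and surgery". It describes the iCare rebound tonometer as one that "is designed not to be influenced by corneal properties". It then gives the permission: "Alternatively, other standard tonometers can be used to measure the intraocular pressure". Goldmann is not excluded from that permission.

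On the device, section 14.1 describes an implant "which shall change the thickness and surface curvature of the" patient's cornea. Section 4.2 states the same purpose. Section 2.2 gives a thickness of about 0.1 mm and an expected gain in mechanical stability.

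The only standardisation across visits is a recommendation on time of day (8.5.4). The surgical data listed in 8.5.7 include the treated eye's IOP but not the tonometer used.

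**The concern.** A change from baseline is interpretable only if the measuring method responds to pressure in the same way before and after surgery. Two things can break that here.

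- **Implant-related shift.** With a tonometer that depends on the cornea, the reading can move because the cornea has changed, with no change in pressure.
- **Between-instrument shift.** If a subject's baseline and follow-up readings come from different tonometers, the difference between instruments enters the change.

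Section 14.2 lists IOP elevation due to the procedure or to steroids as a risk, and steroid drops start after implantation (8.5.3, 8.5.8). An implant-related shift in the readings would begin at about the same time as a real steroid effect. Depending on its sign, it could look like a safety signal or offset one. If the instrument is not recorded, no later analysis can separate the two.

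**Working it through.** **Reasoning from the text**

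1. Section 11.1: Goldmann accuracy depends on corneal thickness, curvature and biomechanics.
2. Sections 2.2, 4.2 and 14.1: the implant is intended to change thickness and/or curvature and is expected to change mechanical behaviour.
3. Section 11.1: a Goldmann or other standard tonometer may be used instead of the iCare.
4. No section fixes the instrument within a subject or between eyes.

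From 1 to 3, a Goldmann reading taken after implantation need not be comparable with one taken before. From 4, instruments may also be mixed.

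The untreated eye is the reference (section 6) and is examined at each visit. It has no implant, so it cannot reveal an implant-related shift. It can offset a change of instrument only if both eyes are measured with the same tonometer at each visit, which is not required.

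**How large an offset would matter**

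The protocol gives no power calculation, no SD for IOP and no bias figure, so there is nothing to reproduce. What follows is an illustration.

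- From the protocol: n = 15 (13.3); two-sided 5% level and 95% intervals (13.7.1).
- Assumed: SD of IOP change of 2, 3 or 4 mmHg; a constant offset of 1 or 2 mmHg in every treated eye; true change zero.
- Simplification: a one-sample t analysis of change, in place of the repeated-measures model.

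Half-width = t(0.975, 14) × SD / √15, with t = 2.145 and √15 = 3.873:

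- SD 2: 2.145 × 2 / 3.873 = 1.11 mmHg
- SD 3: 2.145 × 3 / 3.873 = 1.66 mmHg
- SD 4: 2.145 × 4 / 3.873 = 2.22 mmHg

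The probability of a nominally significant change when the true change is zero comes from the noncentral t distribution with 14 degrees of freedom and noncentrality offset × √15 / SD. For example, 2 mmHg at SD 3 gives 2 × 3.873 / 3 = 2.58.

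| Offset | SD 2 | SD 3 | SD 4 |
|---|---|---|---|
| 1 mmHg | 0.44 | 0.23 | 0.15 |
| 2 mmHg | 0.95 | 0.67 | 0.44 |

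If only 5 of the 15 treated eyes were switched to an instrument reading 1 to 2 mmHg differently, the mean change would move by 5/15 × 1 = 0.33 to 5/15 × 2 = 0.67 mmHg.

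**The case against.** The strongest reply is that this is one site with 15 subjects, a mainly descriptive analysis and nominal p-values. IOP is one of several secondary safety endpoints, and no decision rule rests on an IOP test. Section 11.1 describes the iCare at length and mentions other tonometers only as an alternative; if the iCare is used throughout, its described design largely removes the worry. Central corneal thickness is measured by OCT at the same clinic follow-ups, so IOP change can already be read beside thickness change. The case report form is not shown and may record the instrument.

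Most of this stands and limits the weight of the point. It does not restore consistency: iCare use is not required, Goldmann remains available, and switching is neither prevented nor covered by any rule. Whether switching would be frequent is unknown. The iCare statement is itself a design claim, not evidence of performance over an implant.

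A reader might infer more than the documents support:

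- *That the 0.1 mm implant implies a known shift in mmHg.* The protocol gives no conversion from thickness to pressure, and nothing in it supports a linear one for an implant in a mid-stromal pocket.
- *That a 2 mmHg offset would show as a significant rise.* It would do so with probability 0.67 at SD 3 and 0.44 at SD 4.
- *That the implant compromises the eligibility criterion in 7.2* ("Patients with IOP <10 mmHg or >21 mmHg"). Eligibility is assessed before implantation, so an implant-related shift cannot affect it.

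**Conclusion.** The point holds as a design weakness in section 11.1 that is cheap to correct. The section identifies a source of measurement bias, describes an instrument intended to avoid it, and then makes that instrument optional with no rule on consistency, in a trial whose device is meant to change the corneal properties concerned.

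The size of any shift cannot be derived from the documents. What can be said is that, under an assumed SD of change of 2 to 4 mmHg, the interval half-width is about 1.1 to 2.2 mmHg, so an offset of 1 to 2 mmHg would be of the same order as the precision of the estimate.

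It would go too far to say that the expectation in 14.1 of unimpaired intraocular pressure cannot be examined. It can be examined, but less reliably than with one fixed instrument. The endpoint is secondary and descriptive, and the recommendation should carry corresponding weight.

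**What to change.** In section 11.1, replace the sentence that permits other tonometers with a requirement to use one tonometer type, the iCare already described there, for both eyes of each subject at baseline and at every follow-up. The pre-operative readings on the surgery days should be covered too, because 13.7.1 defines baseline as the last valid value before first treatment. Record the instrument on the case report form.

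If another tonometer has to be used, keep the value and report it in the safety listings, flag it, and show the change-from-baseline summary with and without flagged values. Flagged values should not simply be dropped: with 15 subjects and no imputation (13.7.7), that could discard safety observations at the visits where a raised pressure was being checked.

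Present treated-eye IOP change beside the same-visit change in central corneal thickness and beside the fellow eye. Both are already measured.

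The cost is one sentence in 11.1, one field on the form and one additional summary. The downside is slightly less flexibility when the iCare is unavailable.

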11.2 BEST CORRECTED VISUAL ACUITY

Best Corrected Visual Acuity (BCVA) will be assessed using ETDRS/LogMAR

BCVA will be measured at baseline and at each follow-up visit.

11.3 SLIT LAMP ASSESSMENT AND PHOTOGRAPHY

Slit lamp photography is used to document the microscopic and obscure details of the transparent, translucent and opaque structures of the anterior segment, of the implanted Gebauer[™] Lenticule and surrounding areas of the eye.

Often conditions affecting the anterior segment of the eye are of a subtle nature and can only be documented using a Slit Lamp Bio microscope with an attached camera. Slit Lamp Photography utilizes a variety of magnifications, angles of view and types of illumination to highlight the areas of interest. This is especially useful in following progression or changes in specific pathology such as new vessels, cataracts and pterygium.

The slit lamp photography will be performed at baseline and at each follow-up visit.

The Royal	Document No.	Version	Document Date	Author	Page: 36
Wolverhampton NHS Trust	CIP Study No. 2019OPH108	1.6	03 August 2021	[name]	Out of: 60

11.4 CENTRAL CORNEAL THICKNESS Measurement (OCT)

Optical coherence tomography (OCT) provides high resolution images of the cornea and anterior segment. It is based on the principle of partial coherence interferometry. It has the benefits of being a rapid, non-contact method requiring less expertise to perform. It is capable of visualizing fine corneal structures such as the corneal epithelium, Bowman's layer, and corneal endothelium.

It helps to visualize various cross sections of the cornea and assess the depth and location of the Gebauer[™] Lenticule implant and to discern its relation with the anterior corneal cap and the underlying stromal bed.

Anterior Segment OCT will be performed at baseline and at each follow-up visit.

11.5 CORNEAL TOPOGRAPHY

Corneal topography is a computer assisted diagnostic tool that creates a three-dimensional map of the surface curvature of the cornea.

Topographers can be Placido disc systems or slit-scanning devices.

Placido disc topography systems do not actually measure elevation; rather, they derive anterior corneal elevation data by reconstructing actual anterior curvature measurements via sophisticated algorithms. Slit-scanning or elevation devices directly measure the elevation of both the anterior and posterior cornea via time domain or light-based analysis. Scheimpflug tomographers can analyze the very center of the cornea and image both the anterior and posterior corneal surfaces.

The Pentacam is a hybrid Placido-Scheimpflug device that rotates around the eye 180 degrees in 2 seconds, producing 50 images of both corneal surfaces and 138 000 elevation points to create a 3-D representation of the cornea.

Alternatively, other standard corneal topographers can be used.

Corneal topography will be performed at baseline and at each follow-up visit.

12. STUDY DURATION

The duration of each subject's involvement with the study is expected to be 7-25 months from the time of enrollment and signing of the informed consent document. Each participant will come for treatment/follow-up visits at baseline, procedure day, and all other 4 follow-up visits post procedure. Telephone visits will be conducted 2-weekly up to 3 months. Unscheduled visits may be scheduled additionally if required for medical reasons.

Completion of active enrolment is anticipated to last approximately 1-3 months. The primary endpoints will be achieved when the last study subject has completed his/her 6 months follow-up. For the assessment of long-term tolerability, subjects will be invited to additional follow-up visits after 1 and 2 years. Therefore, the total study duration is 9, respectively, 27 months.
The Royal	Document No.	Version	Document Date	Author	Page: 37
Wolverhampton NHS Trust	CIP Study No. 2019OPH108	1.6	03 August 2021	[name]	Out of: 60

13. STATISTICAL CONSIDERATIONS

13.1 STUDY DESIGN AND OBJECTIVES

The study is planned as an open-label, investigator initiated feasibility clinical study to assess the safety and efficacy of the Gebauer[™] Lenticule implant in subjects suffering from keratoconus or post-LASIK ectasia. Therefore, only 15 patients are intended to be investigated.

13.2 STUDY ENDPOINTS

The primary and secondary clinical endpoints for the evaluation of product safety and effectiveness are listed in detail in Chapter 5 of this Clinical Investigation Plan.

13.3 JUSTIFICATION OF SAMPLE SIZE

The present study is an open-label investigator initiated feasibility clinical study and will mainly be analysed with descriptive statistics. No formal sample size calculation was performed, the sample size of 15 subjects is considered sufficient to enable the estimation of the study endpoints.

13.4 BLINDING

This is an open label study. No blinding of patients and/or investigators is intended.

13.5 DATA ANALYSIS SETS

13.5.1 FULL ANALYSIS SET (FA)

The full analysis set (FA analysis) will consist of all subjects enrolled in the study. All variables described in the Case Report Form will be evaluated systematically

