8.4 SUBJECT ENROLMENT

A Screening/Enrolment Log will be maintained to document selected information about candidates who meet or fail to meet the entry criteria. Subjects meeting all eligibility requirements will be eligible to advance in the study, and they will be assigned a 3 digit Subject Identification Number. If the subject does not meet all of the eligibility requirements, the subject's participation is denied.

All subjects who meet the eligibility requirements will be invited to participate. Subjects will be considered enrolled into the study after:

- 1. A signed Informed Consent has been obtained.
- 2. The subject has met all of the inclusion and none of the exclusion criteria.
- 3. The screening assessments results have been approved by the Chief Investigator

8.5 **PROCEDURAL INFORMATION**

There will be one screening visit followed by the surgical flap creation visit, then the implantation visit and 4 compulsory follow-up study visits. In addition 2 weekly, telephone assessments will be conducted up to 3 months. In addition to that, 2 optional long-term follow-up visits are planned, 1 and 2 years after implantation.

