8.5.6 PROCEDURAL FAILURES

Failure to perform the procedure with the Gebauer[™] Lenticule will be recorded on the CRF as an operative failure. In the event of operative failure to treat or if the surgery had to be terminated unsuccessfully for whatever reasons, a detailed explanation of the circumstances will be recorded and an adverse event form will be filed. The patient will be followed until final decision.

It shall be noted that the Investigator must return any damaged or unused study devices within 24 hours post surgery to the manufacturer of the product, GEBAUER MEDIZINTECHNIK GmbH, [name].

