13.5.2 ANALYSIS SET FOR EFFECTIVENESS (EF)

The effectiveness analysis set will consist of all subjects who were implanted with the Gebauer™ Lenticule.

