13.6 STATISTICAL ANALYSIS OF ANALYSIS SETS

The FA analysis set will serve as the main set for the safety assessments.

The EF analysis set will serve as the main set for the effectiveness assessments.

The Royal	Document No.	Version	Document Date	Author	Page: 38
Wolverhampton NHS Trust	CIP Study No. 2019OPH108	1.6	03 August 2021	[name]	Out of: 60

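### The safety denominator can include patients who were never operated on, and the main analysis of the procedural endpoints leaves out failed implantations

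*Protocol*

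**What the plan says.** Protocol section 13.5.1 defines the first set: "The full analysis set (FA analysis) will consist of all subjects enrolled in the study". It adds: "All variables described in the Case Report Form will be evaluated systematically". Section 13.6 assigns it to safety: "The FA analysis set will serve as the main set for the safety assessments". Section 8.4 fixes the moment of enrolment. "Subjects will be considered enrolled into the study after" three conditions are met: signed consent, eligibility, and the Chief Investigator's approval of the screening results. All three come before surgery. Sections 6, 8.5.2 and 8.5.3 then place pocket or flap creation on Day 0 and implantation up to 30 days later.

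Section 10 rules out removing a subject from the study "unless the subject has withdrawn his/her consent before treatment or no treatment was ever attempted". Section 15.4 says that subjects exposed to study treatment are evaluated for adverse events.

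On the effectiveness side, section 13.5.2 says: "The effectiveness analysis set will consist of all subjects who were implanted with the" lenticule. Section 13.6 adds: "The EF analysis set will serve as the main set for the effectiveness assessments". Section 5.2.4 counts pocket-size suitability, duration of surgery, the investigator's procedure evaluation and post-surgical measures among the secondary effectiveness endpoints. Section 8.5.6 covers failures. "In the event of operative failure to treat or if the surgery had to be terminated unsuccessfully for whatever reasons", the circumstances are documented, an adverse event form is filed and the patient is followed.

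**The concern.** There are two separate problems of denominator.

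First, safety. The primary safety endpoints in section 5.2.1 are signs of rejection after implantation, and treatment-related adverse events during implantation and afterwards. Section 13.7.5 plans a cumulative incidence with a 95% CI for the adverse events. A patient who is enrolled and then drops out before surgery can have neither. Read literally, sections 13.5.1 and 13.6 still count that patient in the denominator. Section 10 points towards leaving such patients out but speaks of the study, not of the analysis set. Two analysts with the same data could therefore report different primary safety rates.

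Second, the procedure. Endpoints that describe how the operation went are analysed mainly in patients in whom it ended with an implant in place. A patient whose implantation was abandoned, for example because the pocket was unsuitable, is outside that set by definition.

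In a feasibility study, the event rate per treated patient and whether the implant can be placed are central answers. Each needs a denominator that matches its question.

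**Working it through.** **Inputs.** Planned size is 15, with no formal calculation (section 13.3), so there is no precision figure to reproduce. Withdrawn subjects may be replaced up to an extra 20% of the original size (section 10): 15 × 0.20 = 3, so at most 15 + 3 = 18 enrolled. The number enrolled but never operated on is not given. I assume k = 0 to 3, using the replacement cap as a guide. Event counts of 3 and 0 are illustrations.

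**Step 1: relative dilution.** With x events and 15 operated patients, the rate per operated patient is x/15 and the rate in the full set is x/(15 + k). The relative fall is 1 − 15/(15 + k), whatever x is.

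| k | Full set | Relative fall | 3 events | 0 events, upper 95% limit |
|---|---|---|---|---|
| 0 | 15 | 0% | 20.0% | 21.8% |
| 1 | 16 | 6.3% | 18.8% | 20.6% |
| 2 | 17 | 11.8% | 17.6% | 19.5% |
| 3 | 18 | 16.7% | 16.7% | 18.5% |

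If the never-operated patients are instead among 15 enrolled and are not replaced, the fall is k/15: 6.7%, 13.3% or 20.0% for k = 1, 2 or 3.

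**Step 2: precision.** Exact (Clopper-Pearson) limits are the 2.5% quantile of Beta(x, n − x + 1) and the 97.5% quantile of Beta(x + 1, n − x). For x = 0 the upper limit is 1 − 0.025^(1/n).

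- 3/15 = 20.0%, CI 4.3 to 48.1, width 43.8 points.
- 3/18 = 16.7%, CI 3.6 to 41.4, width 37.8 points.
- 0/15: 1 − 0.025^(1/15) = 21.8%. 0/18: 1 − 0.025^(1/18) = 18.5%.

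The largest shift in the table is 20.0 − 16.7 = 3.3 points, against intervals about 40 points wide.

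**Step 3: failed implantations.** Suppose 15 operations are attempted and f fail. Among all attempted, the failure proportion is f/15:

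- f = 1: 6.7% (CI 0.2 to 31.9)
- f = 2: 13.3% (1.7 to 40.5)
- f = 3: 20.0% (4.3 to 48.1)

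The effectiveness set then holds 14, 13 or 12 patients, with no failures among them by construction. Unlike the safety dilution, this exclusion takes effect as soon as one implantation fails.

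**Step 4: where the failures still appear.** Section 8.5.6 has them recorded on the CRF as operative failures and filed as adverse events. Section 8.5.7 records overall implantation success, pocket size and the procedure evaluation. Section 13.5.1 has all CRF variables evaluated in the full set, and section 13.7.8 makes the analysis of that set the content of the 6-month report. The omission is therefore confined to the main, implanted-only analysis.

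**The case against.** A reader might infer more than the protocol supports, in four ways.

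- **That the adverse event rate is diluted as a matter of fact.** Dilution needs at least one never-operated patient kept in the full set. It is zero if every enrolled patient is operated on, or if removal under section 10 also takes the patient out of that set. Section 10 may be the remedy rather than a contradiction; the protocol leaves this open. Three such patients is also an extreme case, because replacement covers anyone withdrawn before the 6-month visit, including operated patients.
- **That section 15.4 limits adverse event evaluation to exposed patients.** It says exposed patients will be evaluated; it does not exclude others. Section 15 starts the safety reporting period at the baseline examination, and the schedule in section 8.5.9 marks adverse event documentation at baseline. An enrolled set suits a listing of pre-surgery events.
- **That operative failures disappear, or that an implantation success of 100% would be reported.** Failures remain in the full set (Step 4). No implantation-success proportion is listed in section 5.2.4; success is a CRF variable, and section 13.5.1 has it evaluated with failures present. Section 13.6 calls the implanted set only the main one for effectiveness.
- **That everything leans towards the device.** The full set keeps patients who had a pocket but no implant, and every operative failure generates an adverse event form. Both bring unfavourable cases into the safety analysis.

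It is also fair that the study is mainly descriptive, sets no decision threshold, and will list all adverse events, so a reader could recompute rates in 15 to 18 patients.

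All of this stands as a limit on size and certainty. It does not remove the point. The protocol itself fixes the sets, so this is not a detail left to a later plan. As fixed, one denominator can include patients who cannot have the event, and the main procedural analysis is conditional on success.

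**Conclusion.** The point holds in a limited form. The definitions of the safety set in sections 13.5.1 and 13.6 are not reconciled with sections 8.4, 10 and 15.4. Where a never-operated patient stays in the full set, the incidence of treatment-related events and rejection is understated by a relative 6.3% to 16.7% for one to three such patients added to 15 operated, and not at all if there are none. In absolute terms this is at most 3.3 points in the three-event illustration, small against the sampling uncertainty. The figures rest on the assumed 0 to 3 patients and on illustrative event counts. The main analysis of the procedural endpoints omits failed implantations by definition, although the protocol captures them elsewhere. Both are worth correcting because the correction is cheap and the questions are central to a feasibility study.

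**What to change.** In sections 13.5 and 13.6:

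- Define a safety and procedure set: all subjects in whom pocket or flap creation, or implantation, was attempted. Do not narrow safety to implanted patients, since those with a pocket but no implant carried surgical risk.
- Use this set for the incidence of treatment-related adverse events and rejection in section 13.7.5. To match the denominator, count events from pocket or flap creation onwards. Give the number implanted beside the rejection result, since rejection requires an implant.
- Use the same set for the procedural endpoints in section 5.2.4, with operative failures included and reported as failures.
- List any pre-surgery adverse events for all enrolled subjects.
- Keep the implanted set for K-readings, corneal thickness, best corrected visual acuity and satisfaction.
- Use all enrolled subjects for disposition and baseline, and state whether a subject removed under section 10 stays in that set.

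The cost is a few definitions, with no new data or visits. Reported rates may become slightly less favourable.
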